7.1.6 Secondary endpoints

30-day major adverse events: events that meet one of the following criteria during the study:

- All-cause mortality: death of any cause occurring within 30 days of procedure.
- Intestinal ischemia: lack of sufficient blood flow in the intestine, requiring intensive drug treatment or surgical/intravascular intervention treatment.
- Myocardial infarction: the increase of one or more cardiac biomarkers (especially troponin) with evidence of myocardial ischemia: ECG changes suggesting new ischemia, or imaging evidence.
- Paraplegia: severe paralysis of lower limbs.
- Kidney failure: GFR < 15ml/min, requiring permanent dialysis, renal transplantation, or death due to renal insufficiency.
- Respiratory failure: pneumonia or respiratory failure requiring ventilator support for more than 24 hours after surgery.
- Stroke: symptoms lasting 24 hours due to cerebrovascular diseases such as hemorrhage, embolism or thrombosis.
- Blood loss > 1000 ml: estimated intra-procedural blood loss > 1000 ml.

Immediate technical success: successful introduction and withdrawal of stent graft and delivery system, with accurate positioning of stent graft, normal stent shape, no distortion, bending, stenosis and occlusion, and no accidental coverage of internal iliac artery or visceral artery.

All-cause mortality: death from any cause.

Aneurysm related death: death caused by rupture of abdominal aortic aneurysm or any operation to treat abdominal aortic aneurysm. All deaths shall be judged by the Clinical Events Committee (CEC) to determine the relevance of aneurysm, instruments or surgery.

Secondary intervention: including open and intracavitary intervention. Open surgery: Open surgery performed at any time to address a failure of endovascular treatment due to failure of stent implantation or placement, complications or other clinical conditions, or after the initial success of endovascular treatment. Secondary endovascular intervention: any intravascular surgical intervention performed to resolve complications such as endoleak, aneurysm expansion, stent occlusion, stent migration and stent defect after the implantation of Minos™ system.

Change in aneurysm diameter: including “enlargement”, which refers to an increase of aneurysm diameter greater than 5mm; “reduction”, which refers to a reduction of aneurysm diameter greater than 5mm; and “stable”, which refers to a change in aneurysm diameter less than or equal to 5mm.

Endoleak: recorded after surgery according to imaging appearances. Adjuvant therapy such as balloon dilatation due to intraoperative endoleak shall not be included in the analysis. Type I endoleaks are leaks at the proximal or distal attachment sites. Type II endoleaks are caused by retrograde flow through collateral vessels into the aneurysm sac. Type III endoleaks are holes, defects, or separations in the stent-graft material. Type IV endoleaks represent porous graft walls. Endoleaks observed in the same subject at different follow-up timepoints without and which have not been treated shall be calculated once.

Stent migration: movement of stent greater than 10 mm.

Stent fracture: fracture of the metal wire of the stent framework.

Stent stenosis and occlusion: stenosis of the internal diameter of the covered section of the stent is a narrowing of $\geq 50\%$ as seen on imaging; stent occlusion refers to 100% stenosis of stent detected on imaging.

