3.2 Project contents

The study is designed as a prospective, multi-centre, post-market, real-world observational registry study. Continuous enrollment is to be conducted for all subjects treated with Minos™ Abdominal Aortic Stent-Graft and Delivery System who meet the inclusion criteria and who voluntarily consent to participate in the study. An enrollment duration period of 24 months is expected for this project and initially, 200 subjects (170 in China and at least 30 in Europe) are to be enrolled. Patient follow up – including CT imaging - will be undertaken in accordance with the usual standard of care at participating sites, and is expected to occur at 30 days, 6 months, 12 months and 2-5 years post-procedure.

1. Primary endpoint

- Technical success rate at 12 months

2. Secondary endpoints

- Incidence of major adverse events at 30 days
- Immediate technical success rate
- Incidence of successful aneurysm treatment at 2-5 years
- All-cause mortality up to 5 years post-procedure
- Aortic aneurysm related mortality up to 5 years post-procedure
- Secondary intervention rates up to 5 years post-procedure
- Aneurysm diameter and variation in aneurysm diameter from 30 days to 5 years post-procedure
- Incidence of type I, III endoleaks from 30 days to 5 years post-procedure
- The incidence rate of stent migration, fracture, stenosis, occlusion and distortion from 30 days to 5 years post-procedure

3. Other endpoints: technical success rate of Hercules balloon and incidence of balloon rupture, where applicable.

In this study, immediate technical success rate, technical success rate at 12 months, secondary intervention rate, aneurysm diameter and variation in aneurysm diameter, and the incidence of type I and III endoleaks are used as efficacy indicators of the Minos™ Abdominal Aortic Stent-Graft and Delivery System. The incidence of 30-day major adverse events, all-cause mortality, aneurysm related mortality, stent migration, stent fracture, stenosis, occlusion and distortion are used as safety indicators of the Minos™ Abdominal Aortic Stent-Graft and Delivery System.

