5. This study is an observational study. If the patient undergoes a postoperative CT review before discharge for clinical purposes or as part of the treating institution's standard of care, this imaging examination will be accepted as the 30 days follow up CT, and a further CT scan at 30 days need not be undertaken.

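### Section 7.1.6 names a 30-day major adverse event endpoint but defines it over the whole study, so six of its eight components have no day limit

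*Protocol*

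**What the plan says.** **MAE endpoint.** The Protocol Summary and section 3.2 list "Incidence of major adverse events at 30 days" as a secondary endpoint. Section 3.2 names it again among the safety indicators: "The incidence of 30-day major adverse events, all-cause mortality, aneurysm related mortality" and others. The only definition is in section 7.1.6: "30-day major adverse events: events that meet one of the following criteria during the study". Section 7.1.4 puts each subject's expected participation at 5 years.

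Eight components follow. Death is bounded: "All-cause mortality: death of any cause occurring within 30 days of procedure". Blood loss is tied to the procedure: "estimated intra-procedural blood loss > 1000 ml". Respiratory failure is tied to surgery without a day limit: "pneumonia or respiratory failure requiring ventilator support for more than 24 hours after surgery". The entries for intestinal ischemia, myocardial infarction, paraplegia, kidney failure and stroke say nothing about timing.

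**30-day imaging.** The flow chart in section 7.2 gives the 30-day visit a window of ±7 days. Note 5 says of a CT taken before discharge, for clinical purposes or as local standard of care, that "this imaging examination will be accepted as the 30 days follow up CT", and no further scan is required. Note 3 says that out-of-window CTs are not deviations. The imaging endpoints in section 3.2 start at 30 days, for example "Incidence of type I, III endoleaks from 30 days to 5 years post-procedure".

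**The concern.** The label and the counting rule for a main safety endpoint disagree. Because death alone among the components repeats the 30-day limit, someone applying the text could conclude that the non-fatal components are meant to run longer. Two other sections make that easier. Section 8.2 plans Kaplan-Meier analysis of other safety indicators over follow-up, and section 3.2 makes MAE a safety indicator. Section 8.4 plans analyses at 30 days, 6 months, 12 months and 2 to 5 years, so a literal count could rise at each later data cut while keeping its 30-day name.

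At stake is whether the reported figure is a 30-day rate at all. Section 4 reports a 30-day MAE rate for the earlier study of the device, and section 17 asks for discussion against similar products. Neither can be set beside a figure that pools 30-day deaths with later infarctions and strokes.

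The imaging issue is separate. Where note 5 is used, a finding made before discharge is reported at a time point that the endpoint list treats as the start of the observation period. Sites differ in whether they scan before discharge, so the content of the 30-day imaging row depends on local practice.

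**Working it through.** **1. The protocol's own figure.** Section 4 gives 2/136 for 30-day MAE in the earlier study. 2/136 = 1.47%, which reproduces the stated 1.5%. The exact (Clopper-Pearson) 95% interval is 0.18% to 5.21%. In 200 subjects the same rate gives 200 × 0.015 = 3 events; for 3/200 the exact interval is 0.3% to 4.3%.

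**2. Components by counting period (section 7.1.6).**

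| Component | Limit in its own entry |
|---|---|
| Death | 30 days |
| Blood loss | Intra-procedural |
| Respiratory failure | After surgery, no day given |
| Intestinal ischemia | None |
| Myocardial infarction | None |
| Paraplegia | None |
| Kidney failure | None |
| Stroke | None |

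So 2 of 8 are bounded, 1 is loosely bounded and 5 are unbounded. For the last six, the only period stated in the definition is the study itself, which is 5 years per subject.

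**3. What the literal reading could do.** The protocol gives no late rate for these components, so this step is an illustration under an assumed combined rate r. Start from 1.5% by day 30 and add first events from day 30 to year 5, which is 5 − 30/365.25 = 4.918 years:

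(a) ignoring death and loss to follow-up: 1 − (1 − 0.015) × exp(−4.918 r)

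(b) letting death end risk: 0.015 + 0.985 × r/(r + m) × [1 − exp(−4.918 (r + m))]

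In (b), m = −ln(126/136) = 0.0764 per year, from the 12-month all-cause mortality of 10/136 in section 4, carried forward unchanged (also an assumption).

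| Assumed r per year | (a) 5-year figure | (a) of 200 | (b) 5-year figure | (b) of 200 |
|---|---|---|---|---|
| 0.5% | 3.9% | 8 | 3.5% | 7 |
| 1% | 6.2% | 12 | 5.5% | 11 |
| 2% | 10.7% | 21 | 9.2% | 18 |
| 3% | 15.0% | 30 | 12.8% | 26 |
| 5% | 23.0% | 46 | 19.5% | 39 |

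Both versions include the early 1.5%, so they describe the whole composite on the same footing as the starting figure. Even the lowest entry is more than twice 1.5%, but the spread shows that r drives the result.

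**4. Imaging time point.** 30 ± 7 days is day 23 to day 37. A CT accepted under note 5 falls before discharge, whenever that is. The protocol gives neither a length of stay nor the share of subjects scanned before discharge, so neither the size of the shift nor the number affected can be computed.

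**The case against.** The strongest reply is that nobody would misread this. The endpoint is called a 30-day endpoint in the Protocol Summary, twice in section 3.2 and in the label of the definition itself. Death is limited to 30 days, blood loss belongs to the procedure, and section 8.4 plans an analysis at 30 days. A reader might infer that the protocol has made MAE a 5-year endpoint, or that its 30-day endpoints are not 30-day at all. The documents do not support that: one loose phrase stands against every other mention. This part of the objection stands, and it makes the fault a contradiction in wording. It does not remove the fault, because the loose phrase sits in the only definition and six components have no day limit of their own to override it.

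It is also fair to say that the study is descriptive (section 8.3), so no sample size or error rate changes. The late event rates are assumed, and the protocol does not give the MAE definition behind the earlier 1.5%.

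On imaging, a reader might infer that the CT rule undermines the MAE rate. It cannot, because every MAE component is a clinical event. Nor does the text show by how many weeks the scans are early. Note 5 is openly stated and follows from standard-of-care imaging. Its reach is limited further: section 7.1.6 counts a persisting untreated endoleak once, and section 7.1.5 concerns only continuous type I and III leaks. Nor does note 5 forbid a later scan. What remains is that a pre-discharge result carries a 30-day label.

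**Conclusion.** The point holds as an internal contradiction in section 7.1.6. The definition, followed as written, does not yield the 30-day rate that the endpoint list promises. The intended meaning is clear enough that the correction involves no design decision.

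The possible inflation cannot be fixed from the protocol. The range of about 3.5% to 23% over 5 years, against 1.5% at 30 days, rests wholly on assumed late rates of 0.5% to 5% per year and a constant hazard. It shows that the wording matters and does not predict what the registry will find.

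The pre-discharge CT rule is a secondary and separate labelling matter. It conflicts with the ±7-day window and with imaging endpoints that start at 30 days, it applies only to subjects scanned before discharge, and its size is unknown.

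**What to change.** **MAE (section 7.1.6).** Replace the study-long counting period in the opening line with one of 30 days from the procedure, stated to apply to all components. Report later events of the same kinds as AEs or SAEs.

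**Imaging (section 7.2, note 5, and the same note in the Protocol Summary).** Leave the scanning permission as it is. Record the actual day of each scan, label pre-discharge scans as such, and report the 30-day endoleak, diameter and device-integrity results with and without them. Do not confine the main result to days 23 to 37. That would discard scans that note 3 accepts and would remove subjects from sites that scan before discharge, leaving missing data that depend on site practice.

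**Cost.** A wording change and one extra table row. No scan is added or withdrawn, and the sample size is unaffected.

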The presence of proximal endoleaks, and amount of vessel wall apposition will be assessed via immediate post-deployment angiography to determine whether balloon dilatation is indicated. The brand type of balloon will be voluntarily selected by investigators. If the Hercules balloon is used, data pertaining to the Hercules balloon shall be recorded. The success rate of Hercules balloon technique and the rate of balloon rupture are used as efficacy and safety indexes for Hercules balloon device. All relevant data will be collected and analysed from time to time as the study progress.

4、 Study background

Abdominal Aortic Aneurysm (AAA) refers to the localized expansion of abdominal aorta exceeding 50% of the diameter of normal abdominal aorta, of which the main complication is rupture and bleeding, and once ruptured, the mortality is about 90%¹. The incidence rate of abdominal aortic aneurysm is growing year by year. Among the Asian population over 50 years old, the incidence rate of abdominal aortic aneurysm is 25.6%/100,000 in males and is 7.6%/100,000 in females; the incidence in men is about 3.5 times that of women². There is no AAA-related epidemiological data in China, but the detection rate of abdominal aortic aneurysm in China is also increasing year by year with the aging of the population, the application of various imaging techniques and the improvement of clinical understanding.

Currently, clinical surgical treatments of subrenal AAAs mainly include traditional open surgery and endovascular abdominal aortic aneurysm repair (EVAR). Traditional open surgery has the disadvantages of massive trauma and many types of complications. It is usually not considered suitable for patients with heart, lung, kidney, brain and other organ lesions. In 1991, Parodi first reported the application of EVAR in the treatment of AAA. Compared with traditional surgery, it can minimize the degree of surgical invasiveness and reduce the surgical risk, so that the frail and ill patients with AAA can access their therapies and achieve better curative effect. It has become the preferred treatment for most patients³⁻⁵.

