13.1 Definition of Adverse Events and solutions

Adverse Event (AE) refers to any untoward medical occurrence during treatment of subjects with the investigational medical device, whether or not considered related to the device.

Device defects refer to unreasonable risks that may endanger human health and life safety under normal use of medical devices, such as label errors, quality problems, faults, etc.

Device related adverse events refer to complications related to the use of the investigational device, including deployment failure of stent and/or conversion to surgery, intra-operative bleeding, perforation or rupture of arterial wall, dissection or thrombus of access vessels, hematoma of the access vessels, pseudoaneurysm of the access vessels, infection of the access site, fever of unknown origin, aneurysm rupture, type I/III endoleak, stent migration, stent infection, limb stent-graft occlusion, pelvic or leg ischemia etc.

Any adverse events that occur during the study must be carefully recorded in the adverse event form. The investigators should provide targeted treatment for adverse events in accordance with local standards of care.

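### Immediate technical success has no seal criterion, and the rule excluding adjuncts for intraoperative endoleak has unclear scope, so this indicator can favour the device

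*Protocol*

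**What the plan says.** Protocol 7.1.6 contains the only definition of technical success for the stent-graft. It opens "Immediate technical success: successful introduction and withdrawal of stent graft and delivery system, with accurate positioning of stent graft" and continues "normal stent shape, no distortion, bending, stenosis and occlusion, and no accidental coverage of internal iliac artery or visceral artery". Section 3.2 lists this measure among the efficacy indicators.

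Section 3.2 also describes an intraoperative check of seal: "The presence of proximal endoleaks, and amount of vessel wall apposition will be assessed via immediate post-deployment angiography". The result decides whether ballooning is indicated. The investigator chooses the balloon brand, and the only balloon-specific recording rule is "If the Hercules balloon is used, data pertaining to the Hercules balloon shall be recorded".

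The endoleak definition in 7.1.6 begins "Endoleak: recorded after surgery according to imaging appearances" and then states "Adjuvant therapy such as balloon dilatation due to intraoperative endoleak shall not be included in the analysis". In the endpoint lists (Protocol Summary and 3.2), incidence of type I and III endoleak is counted from 30 days to 5 years.

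Three other places bear on the same patients:
- Section 7.1.5 fails a subject who has a continuous type I or III endoleak after the operation, or a secondary intervention because of endoleak.
- Section 13.1 includes "type I/III endoleak, stent migration, stent infection, limb stent-graft occlusion" in its list of device-related adverse events.
- The flow chart in 7.2 evaluates adverse events from the intraoperative visit and requires an operation record.

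**The concern.** Section 5.3 says the graft works by isolating the aneurysm from the circulation. A type I or III leak at the end of the procedure means that this has not been achieved. The immediate endpoint tests delivery, position, shape, patency and branch coverage, but not seal. The seal check in the operating room guides ballooning and then enters no stated efficacy endpoint.

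The exclusion sentence adds to this. If it covers all analyses, a reader of the results could not tell how many grafts sealed unaided and how many needed an adjunct. Section 7.1.1 sets out to assess effectiveness and to identify emerging risks, and both call for that information. The error has one direction: leaving out a failure condition can only raise the success rate.

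**Working it through.** **No figure to reproduce.** The protocol states no expected rate for immediate technical success or intraoperative endoleak, and 8.3 says the 200 subjects were not set on statistical grounds. The check is therefore of the definitions, with a scale calculation after it.

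**Step 1: follow two hypothetical subjects through the definitions.** Both meet every delivery, position, shape, patency and branch-coverage condition.

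| Measure | A: type I leak still present when the procedure ends | B: intraoperative type I leak, sealed after an adjunct |
|---|---|---|
| Immediate technical success (7.1.6) | Success | Success |
| Endoleak incidence (3.2, from 30 days) | Counted only if seen on imaging at 30 days or later | Not counted |
| Adjunct for the leak (7.1.6, endoleak) | None given | Excluded; scope unclear |
| Successful aneurysm treatment (7.1.5) | Fails if the leak is continuous | Not failed by the sealed leak |
| Device-related adverse event (13.1, 7.2) | Can be reported | Can be reported |

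On the immediate endpoint, neither subject differs from one whose graft sealed at once.

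**Step 2: two readings of the exclusion sentence.**
- *Narrow:* it belongs to the endoleak definition and says only that ballooning for an intraoperative leak is not an endoleak event.
- *Broad:* it removes such adjuncts from every analysis.

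The text supports either. The definition of secondary intervention in 7.1.6 adds a further doubt: it covers endovascular treatment of an endoleak after implantation, so an adjunct in the same procedure could be counted there or excluded here. On both readings the seal criterion is still missing.

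**Step 3: scale.** Inputs: n = 200 (8.3) and exact binomial 95% intervals (8.2). The leak rate r at the end of the procedure is an assumption, shown over a range. Suppose first that all 200 subjects meet the mechanical conditions. As defined, success is 200/200 = 100% (98.2 to 100). With a seal condition, success is (200 − 200r)/200. For x successes, the limits are the 2.5% point of Beta(x, n − x + 1) and the 97.5% point of Beta(x + 1, n − x).

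| Assumed r | Leaks | Success with seal required | Exact 95% interval |
|---|---|---|---|
| 2% | 4 | 196/200 = 98.0% | 95.0 to 99.5 |
| 5% | 10 | 190/200 = 95.0% | 91.0 to 97.6 |
| 10% | 20 | 180/200 = 90.0% | 85.0 to 93.8 |

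If instead 4 subjects fail mechanically and the leaks occur in other subjects, success as defined is 196/200 = 98.0%. With seal required it becomes 96.0%, 93.0% and 88.0%, the same falls of 2, 5 and 10 points. Any overlap between mechanical failures and leaks makes the fall smaller. In general, each 1% of leaks moves 0.01 × 200 = 2 subjects, or 1 percentage point. The same arithmetic applies to adjunct use if success is split into unassisted and assisted.

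**The case against.** The strongest reply is that the protocol captures these events elsewhere, and much of it stands.

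- **A reader might infer that intraoperative rescue disappears from the study.** The documents do not support that. Section 7.2 collects intraoperative data and an operation record for every subject. Type I/III endoleak is a listed device-related event, and 8.2 reports those events by count and by subject. Open surgery for failed implantation or placement counts as secondary intervention.
- **A reader might infer that balloons of other brands go unrecorded.** The protocol does not say so, and the eCRF is not shown. What can be said is that only the Hercules balloon has a stated recording rule and its own endpoints.
- **A reader might infer that a leaking graft passes the primary endpoint.** Section 7.1.5 builds on technical success but separately fails a continuous type I or III leak and reintervention for endoleak. A persistent leak can therefore still fail. This protection is partial: continuous is not defined, and missing imaging is not a deviation.
- **A reader might see the safety and efficacy results as contradictory.** They are different measures. A procedure can meet the mechanical criteria and still have an adverse event.
- **A reader might take the exclusion to cover cuffs, stents or embolisation.** The sentence names only balloon dilatation as an example, and the CUFF stent-graft is a component of the system (5.2).
- **A reader might assume that a final angiogram is already specified.** The angiogram in 3.2 precedes ballooning. The protocol specifies none afterwards, and the blinded reading in 7.1.3 is for follow-up imaging.

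None of these supplies a seal criterion for the immediate endpoint or settles the scope of the exclusion. Both are fixed in the protocol, so a statistical analysis plan that follows it would inherit them.

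**Conclusion.** The point holds for the immediate endpoint. Immediate technical success, as defined, counts a graft with a type I/III leak at the end of the procedure, or one sealed only after an adjunct, as a success. This efficacy indicator can therefore be biased in the device's favour. The exclusion sentence is ambiguous and needs rewording on either reading.

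The effect on later endpoints is limited by 7.1.5 and by adverse event reporting. The conclusion that the primary result is compromised is not supported. The size of the bias cannot be known from the documents: it is 1 percentage point per 1% of leaking grafts among subjects who otherwise qualify, and the 2% to 10% range above is illustration only. The missing criterion rests on the text alone; the scale rests on the assumed rates and on how far leaks overlap with mechanical failures. The sponsor should make the change, although nothing here invalidates the registry.

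**What to change.** 1. In 7.1.6, add to immediate technical success the absence of type I or III endoleak on the final intraoperative angiogram, where one was obtained. Alternatively, keep the definition and report success with and without that condition. In either case, state how many subjects had no final angiogram.
2. Reword the exclusion sentence: adjuncts for an intraoperative endoleak are not counted as endoleak events or as secondary interventions, but they are tabulated, and immediate technical success is shown with and without adjunct.
3. In 3.2 and on the operation record, capture any balloon or other adjunct and the reason for it, whatever the brand.

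These changes concern recording and reporting only and alter no patient care. The cost is protocol wording, a few eCRF fields, an extra reported line and a somewhat lower headline success figure. For subjects already treated, the new fields depend on what the operation record holds.
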